The UroNav fusion biopsy system until recently *only* allowed targeted prostate biopsy to be performed transrectally. With over 200 devices sold in the United States, UroNav is the most commonly used targeted biopsy system and has been extensively studied by the National Institutes of Health (NIH). UroNav requires pre-biopsy mpMRI for lesion(s) delineation, real-time TRUS registered to the mpMRI and electromagnetic tracking of biopsy needles for precise guidance. The actual working elements of the UroNav fusion biopsy system includes the UroNav mobile workstation cart, ultrasound cart and the electromagnetic field generator which connects to the patient bed by a mobile arm. The electromagnetic field generator in combination with a navigation sensor mounted to the TRUS transducer merges the mpMRI images with live TRUS guidance to accurately biopsy the prostate. As previously mentioned, UroNav provides support for transrectal biopsy procedures but *now* has the capability to perform biopsy via a transperineal approach. The UroNav fusion-guidance for transperineal biopsy requires the transperineal stepper which holds the TRUS probe and a standard biopsy grid plate equipped with UroNav universal sensors to precisely perform biopsies. Invivo supports both UroNav and DynaCad which UTMB has recently acquired and the Department of Radiology currently has been working with for many years, respectively. DynaCad is a software used in the radiology suite which exports diagnostic 3D information from a prior mpMRI exam to discern the prostate gland and MR-suspicious lesions. The transperineal approach (skin halfway between scrotum and anus) essentially eliminates the risk of sepsis and/or infection associated with transrectal prostate biopsy samples obtained through feces and rectal mucosa. Sepsis occurs in up to 3% of patients who undergo transrectal prostate biopsy (Table 1).¹²

Table 1. Signs and Symptoms of Sepsis¹²

General Fever (>38.3°C) Hypothermia (<36°C) Tachycardia >90/min Tachypnea Hypotension (SBP<90 mmHg) Altered mental status Significant edema or positive fluid balance Oliguria Ileus Altered mental status/lethargy
 
Laboratory Normal WBC with >10% immature forms Creatinine increase >0.5 mg/dL INR >1.5 or aPTT >60 secs

Thrombocytopenia (platelet count <100,000/mm³)
Hyperglycemia (plasma glucose >120 mg/dL) in the absence of diabetes
Hyperlactatemia (>1 mmol/L)

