No study has compared UroNav transperineal mpMRI-targeted versus standard transrectal prostate biopsy in the detection of prostate cancer.

The **hypothesis** being tested is that computerized fusion guided biopsy (**UroNav**) will increase detection of csPCa compared to standard biopsy (SB) (transrectal) alone. The primary end point will be the comparison of detection rates csPCa between arm A mpMRI+ and arm B (refer to figure on page 9). csPCa will be defined according to the Standards of Reporting for MRI-targeted Biopsy Studies (START) criteria for targeted biopsy Gleason Score ≥ 7 or maximum cancer core length (CCL) ≥ 5 mm and the updated Epstein criteria for SB (Gleason score ≥ 7 , PSA density ≥ 0.15 , Gleason score ≥ 2 positive cores, and bilateral cancer).^{2,3} The secondary end points will be (1) comparison of the overall detection rate of PCa and csPCa between arm A mpMRI+, arm A mpMRI-, and arm B and (2) comparison of complication rates (Table 2) between arm A mpMRI+ and arm B.

Considering 10% of patients will be lost to follow-up, the total sample size needed will be 80 patients (See Section 9.1 Statistical Considerations). The clinical trial is enrolled in clinicaltrials.gov (**ClinicalTrials.gov Identifier NCT03044197**).

If the primary end point is reached, the study will continue and remain ongoing to examine the remaining secondary end points.

Specific Aims:

1. Determine if UroNav increases the detection of csPCa between arm A mpMRI+ than arm B standard transrectal biopsy.
2. Determine if UroNav increases the overall detection of PCa between arm A mpMRI+ versus arm A mpMRI- and arm B standard transrectal biopsy.
3. Determine if UroNav decreases rates of complications between arm A mpMRI+ than arm B standard transrectal biopsy.

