5.0 Study Procedures

Study population and design:

Eligible patients referred to the Division of Urology will be randomly assigned to one of the following arms: **arm A (mpMRI+ group)**, mpMRI prior to transperineal mpMRI-targeted prostate biopsy; **arm B (Standard group)**, TRUS-guided transrectal 12-core prostate biopsy.

In arm A, all patients with positive mpMRI evidence of lesions suspicious for PCa, i.e. PI RADS ≥ 3 will be submitted to transperineal MRI-targeted prostate biopsy (arm A mpMRI+). In cases of negative mpMRI results i.e. PI RADS < 3, arm A patients will

undergo TRUS-guided transrectal 12-core prostate biopsy (arm A mpMRI-)(refer to figure on page 9).

[figure not shown]
The present randomized clinical trial will compare the outcomes between the two arms.

Primary End-Points: The primary end point will be the comparison of detection rates csPCa between arm A mpMRI+ and arm B. csPCa will be defined according to the Standards of Reporting for MRI-targeted Biopsy Studies (START) criteria for targeted biopsy Gleason Score ≥ 7 or maximum cancer core length (CCL) ≥ 5 mm and the updated Epstein criteria for standard biopsy (Gleason score ≥ 7 , PSA density ≥ 0.15 , Gleason score ≥ 2 positive cores, and bilateral cancer).^{2,3} Patients will be enrolled in an intention to treat trial (See Section 9.1 Statistical Considerations).

Secondary End-Points: The secondary end points will be:

- i. Comparison of the overall detection rate of PCa and csPCa between arm A mpMRI+, arm A mpMRI-, and arm B and
- ii. Comparison of complication rates (Table 2) between arm A mpMRI+ and arm B.

If the primary end point is reached, the study will continue and remain ongoing to examine the remaining secondary end points.

Patients will be consented by Urology providers (IRB approved Co-Investigators and collaborators).

Randomization and data collection will be done by [REDACTED] [REDACTED] (study coordinator) into a REDCap generated case form (SEE APPENDIX). Study coordinator will provide de-identified data for statistical data analysis and will have master file, in password protected computer, which will link the PHI to subject ID (will be assigned by the study coordinator). After the completion of statistical analysis the master file will be deleted permanently.

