- Maximum cancer core length (mm)- Based on the biopsy report will be available 2-4 weeks post-procedure
- Adverse event assessment- Can be done by telephone or clinical visit, usually 2-4 weeks post biopsy procedure

Table 2. Schedule of Events

Variables (Both Arm A and Arm B)	Pre-Study (within 2 months from consent and randomization)	Biopsy	Post-Biopsy Follow-up/Study End (within 2-4 wks from biopsy) Follow-up can be done by telephone or clinical visit)
Informed consent*	X		
Demographics	X		
Medical History	X		
Surgical History	X		
Clinical Stage/digital rectal exam	X		
Vital signs	X		
Height	X		
Weight	X		
PSA	X		
MRI PI-RADS (Arm A)	X	X	
Gland volume (MRI- Arm A or US- Arm B)	X	X	
Diagnosis of Prostate Cancer			X
Serum creatinine***	X		
Diagnosis of Clinically Significant Prostate Cancer**			X
Gleason score			X
Total cancer core length (mm)			X
Maximum cancer core length (mm)			X
UADE*		X	X

* Indicates study-only activity.

All other procedures/tasks are standard of care. Prostate specific antigen (PSA), Digital rectal examination (DRE), Prostate Imaging Reporting and Data System (PI-RADS), transrectal ultrasound (TRUS), Unanticipated Adverse Device Event

**Clinically significant PCa defined as targeted biopsy Gleason Score \geq or maximum CCL \geq 5 mm and the updated Epstein criteria for SB.

*** The serum creatinine assessment will be performed no more than one month prior to randomization.

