7.0 Adverse Events or Unanticipated Problems involving Risk to Participants or Others

Table 3. Complications associated with prostate biopsy

Common (greater than 1 in 10)	Occasional (between 1 in 10 and 1 in 50)	Rare (less than 1 in 50)

 •Blood in your urine for up to 10 days. •Blood in your semen for up to 6 weeks; this is harmless and poses no risk to you or any sexual partners. •Bruising in your perineal area. •Urinary infection (10% risk). •Sensation of discomfort due to bruising. •Haemorrhage(bleeding) preventing you from passing urine (2% risk). 	
 •Blood infection (septicaemia) needing hospitalisation (2% risk). •Haemorrhage (bleeding) needing hospitalisation (1% risk). •Failure to detect a significant cancer of the prostate. •The procedure may need to be repeated if the biopsies are inconclusive or your PSA level rises further. •Inability to pass urine (retention of urine). 	
 •Hospital-acquired infection •Colonisation with MRSA (0.9% - 1 in 110). •MRSA bloodstream infection (0.02% - 1 in 5000). •Clostridium difficile bowel infection (0.01% - 1 in 10,000). 
Please note: The rates for hospital-acquired infection may be greater in “high-risk” patients. This group includes, for example, patients with long-term drainage tubes, patients who have had their bladder removed due to cancer, patients who have had a

		long stay in hospital or patients who have been admitted to hospital many times.
--	--	----------------------------------------------------------------------------------

Complications associated with MR-Gadolinium:

The contrast material used in MRI called gadolinium is less likely to produce an allergic reaction than the iodine-based materials used for x-rays and CT scanning. Very rarely, patients are allergic to gadolinium-based contrast materials and experience hives and itchy eyes. Reactions usually are mild and easily controlled by medication. Severe reactions are rare.

Nephrogenic systemic fibrosis (NSF), a thickening of the skin, organs and other tissues, is a rare complication in patients with kidney disease that undergo an MR with contrast material. Gadolinium-based contrast material may be withheld in some patients with severe kidney disease.

Adverse Event:

For the purposes of this study, pre-planned interventions noted at baseline are not considered AEs.

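### The single post-biopsy complication contact may be by telephone or clinic visit with no rule for which, so the Aim 3 complication rates could be ascertained unequally between groups

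*Combined protocol and SAP*

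**What the plan says.** Section 2.0 states Aim 3 as: "Determine if UroNav decreases rates of complications between arm A mpMRI+ than arm B standard transrectal biopsy". Section 5.0 lists the matching secondary endpoint: "Comparison of complication rates (Table 2) between arm A mpMRI+ and arm B".

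The post-procedure part of Section 5.0 describes the follow-up: "Adverse event assessment- Can be done by telephone or clinical visit, usually 2-4 weeks post biopsy procedure". The heading of that part and the last column header of Table 2 repeat the choice of telephone or visit. The available text does not say which mode applies to whom, or who decides. The same list puts the biopsy report at 2-4 weeks after the procedure.

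Table 2 is one schedule for both arms. It marks vital signs and creatinine at the pre-study column only ("The serum creatinine assessment will be performed no more than one month prior to randomization"), and its only safety row at biopsy and follow-up is UADE.

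Section 9.0 describes the trial as un-blinded and plans Fisher's exact test, two-sided at 5%, for categorical variables.

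**The concern.** A complication rate depends on how hard one looks. A visit allows examination and open questioning; a call depends on what is asked and recalled. If the mode varies from man to man, the same true event may be counted in one man and missed in another. That is harmless on average if the mode is unrelated to the group, but nothing in the plan ensures this. Staff know the arm and may know the diagnosis when the contact is made, and the plan expects more cancers in arm A. Men with cancer may be more likely to be asked in.

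If so, extra complications would be recorded in arm A, against the direction Aim 3 hopes to show. If the mode followed the group for some other reason, the false difference could go either way. It could not be repaired after follow-up ends.

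**Working it through.** The plan states no power or sample size for complications, so there is no figure of its own to reproduce. The group sizes come from Section 9.0.

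**Group sizes.** Aim 2 needs 72 men, 36 per arm; 72 / 0.90 = 80 reproduces the stated total with 10% loss. About 25% of arm A is assumed MRI-negative, so arm A mpMRI+ has about 0.75 × 36 = 27 men. The Aim 3 comparison is therefore about 27 vs 36.

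**Assumptions that the documents do not give.** A visit finds 90% of events. A call finds 50%, with a range up to 70%. Every man with any cancer is seen in clinic and every other man is telephoned. The clinic shares are then the overall detection rates that Section 1.0 quotes from a cited randomised trial: 50.5% for targeted biopsy and 29.5% for standard biopsy, 21 points apart.

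**Formula.** Recorded rate = true rate × (clinic share × visit sensitivity + telephone share × call sensitivity). The true rate is set equal in both groups, so any gap is spurious.

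| True rate | Call sensitivity | Arm A mpMRI+ | Arm B | Spurious gap |
|---|---|---|---|---|
| 10% | 50% | 0.10 × (0.505 × 0.9 + 0.495 × 0.5) = 7.02% | 0.10 × (0.295 × 0.9 + 0.705 × 0.5) = 6.18% | 0.84 points |
| 10% | 70% | 8.01% | 7.59% | 0.42 points |
| 50% | 50% | 35.1% | 30.9% | 4.2 points |
| 50% | 70% | 40.05% | 37.95% | 2.1 points |

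The 10% rate is the risk that Table 3 gives for urinary infection. The 50% rate is an assumed value for a common minor effect.

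**Effect on the test.** This is the exact rejection probability of the two-sided Fisher test at 5%, with no true difference:

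| Recorded rates (A mpMRI+ vs B) | 27 vs 36 | 36 vs 36 |
|---|---|---|
| 35.1% vs 30.9% (largest gap above) | 4.6% | 3.9% |
| 45% vs 25% (A all in clinic, B all by telephone) | 32% | 34% |
| 25% vs 45% (the reverse) | 34% | 34% |
| 45% vs 45% (equal ascertainment) | 4.1% | 2.5% |

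The extreme rows use a true rate of 50%: 0.50 × 0.9 = 45% and 0.50 × 0.5 = 25%. The 36 vs 36 column is for reference, because Aim 3 leaves out the MRI-negative men.

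**Size as a limit.** In 36 arm B men one expects 36 × 0.10 = 3.6 urinary infections and 36 × 0.03 = 1.1 cases of sepsis (Section 2.0 gives up to 3%). Even at 10% vs 0%, Fisher's power at 27 vs 36 is about 15%.

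**The case against.** The strongest reply is that the plan treats both arms alike: one schedule, one window and the same choice of mode. Nothing says that the mode follows arm or diagnosis. That stands, and it makes this a risk only. Under the diagnosis-driven assumption the test stays below its nominal 5%, and the 32-34% needs a complete split that the documents nowhere suggest. Small numbers limit Aim 3 more than this bias does.

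A reader might infer that infection and sepsis cannot be measured at all, because Table 1 describes sepsis by vital signs and laboratory values and none is scheduled after biopsy. The documents do not support that:

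- Table 1 is background in the rationale; no section makes it an endpoint definition.
- Table 3 lists septicaemia as needing hospitalisation, which meets the SAE definition in Section 7.0 whatever the mode of contact.
- Most of the common Table 3 items, bruising included, can be reported by telephone.
- Sepsis is acute, so tests at one contact 2-4 weeks later would not reliably show an episode already treated.

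The REDCap case form is in an appendix not available here and may hold a structured checklist. That could reduce the concern, but it would not settle the mode that the protocol text leaves open. Section 5.0 has the coordinator extracting data from patient records, but describes this for biopsy reports and does not state its use for complications.

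**Conclusion.** The concern holds in limited form. The mode of the only post-biopsy complication contact is open, staff are not blinded, and the result arrives in the same window, so unequal ascertainment is possible in the Aim 3 comparison. It is not a documented arm difference.

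On the assumed sensitivities and cancer-to-clinic sorting, the false gap is under 1 point for a 10% complication and 2.1-4.2 points for a 50% one, with little effect on the test. Serious inflation (32-34% against 4.1%) appears only at the extreme. The documents give no figures for sensitivity or for the split of modes, so all these sizes are illustrations.

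This is a cheap improvement for a secondary endpoint. It does not threaten the primary result.

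**What to change.** In the post-procedure part of Section 5.0 and in Table 2:

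1. Use one mode for the compared rate in both arms: the same scripted complication checklist, by telephone, at the same time point, completed before the pathology result is given where feasible.
2. Write down definitions of urinary infection and sepsis. Score both from Epic, and from any outside records the man reports, over the same window in both arms.
3. Keep events found only at other visits in safety reporting, but outside the compared rate.
4. Reconcile which complications are collected. The endpoint cites Table 2, which is the schedule, while the complications are in Table 3. Section 7.0 both limits AE collection to death and serious injury and calls for all AEs. A standard call does little until this is settled.

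The cost is a wording change, a short call script and somewhat more record extraction by the coordinator, with no extra visit or test. The downside is that minor signs seen only on examination leave the compared rate.

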(PI). All patients will receive one dose fluoroquinolone antibiotic to be taken the morning of prostate biopsy (if fluoroquinolone allergy then may substitute Bactrim DS, if prior documented UTI(s) in past then antibiotic may be tailored according to those culture(s) sensitivities) to cover enteric flora. All patients will receive an enema until result to be performed the morning of prostate biopsy.

Urologists will obtain SOC informed consent and perform the TRUS biopsies.

The 12 cores will be obtained from 12 separate anatomical regions of the prostate which is standard practice in performing TRUS-guided transrectal prostate biopsy: left medial apex, left lateral apex, left medial midgland, left lateral midgland, left medial base, left lateral base, right medial apex, right lateral apex, right medial midgland, right lateral midgland, right medial base and right lateral base.

For arm A and arm B biopsy, [REDACTED] (the study research coordinator) , [name] and [name] (Chairman, Division of Urology and study co-investigator), will monitor safety and any possible Unanticipated Adverse Device Events (UADEs). Serious Adverse Events (SAEs), Adverse Events (AEs) and UADEs assessment will be done by [name].

For Arm A and Arm B biopsy, the procedure will be performed and the sample will be sent to the Pathology lab for analysis. [name] and other urology providers will not be involved with the sample analysis and biopsy report data and results. Once the report / data is available on Epic for review, the study coordinator will extract data from patient records/ Epic into an electronic data sheet (REDCap case form, SEE APPENDIX) on which the patient will be identified by a subject ID assigned to them, no PHI information will be present. The data analysis will be performed in aggregate. A master file linking the patient to Subject ID will remain with the study coordinator for data entry purposes and once the data analysis is complete, the master file will be securely stored and password protected.

- Adverse event assessment (Tables 2 and 3)

POST-PROCEDURE EVALUATION/ END OF STUDY- (Follow-up can be done by telephone or clinical visit)

- Diagnosis of csPCa- Based on the biopsy report will be available 2-4 weeks post-procedure
- Gleason score ((Grade System to classifying PCa)- Based on the biopsy report will be available 2-4 weeks post-procedure
- Total cancer core length (mm)- Based on the biopsy report will be available 2-4 weeks post-procedure

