Adverse Events (AEs) collected in this study will be limited to death post biopsy procedure, serious injury (life threatening, results in permanent impairment of body functions or permanent damage to a body structure, or necessitates medical or surgical intervention to preclude permanent impairment of body functions),

Any unanticipated adverse device event will be recorded and reported to the IRB within 10 business days.

AE/SAE information must be collected up until subject's completion of the study. In the case of death or serious injury, Investigator or study coordinator must report to IRB as soon as possible within 10 business days after first learning the event.

Collection of all AEs, to be reported as follows:

- i) all serious adverse events and/or unanticipated problems involving subjects will be reported as required per the UTMB IRB Policies and Procedures, Section 8; and
- ii) All other adverse events will be recorded on an excel spreadsheet and submitted with each continuing review.

Serious Adverse Event (SAE):

An SAE is defined as an AE that meets one of the following conditions:

- Death during the period of protocol defined surveillance
- Life-threatening event (defined as a subject at immediate risk of death at the time of the event)
- An event requiring inpatient hospitalization or prolongation of existing hospitalization during the period of protocol defined surveillance
- Results in congenital anomaly or birth defect
- Results in a persistent or significant disability/incapacity
- Any other important medical event that may not result in death, be life threatening, or require hospitalization, may be considered a serious adverse experience when, based upon appropriate medical judgment, the event may jeopardize the subject and may require medical or surgical intervention to prevent one of the outcomes listed above. Examples of such medical events include allergic bronchospasm requiring intensive treatment in an emergency room or at home, blood dyscrasias or convulsions that do not result in inpatient hospitalization, or the development of drug dependency or drug abuse.

All SAEs will be:

- recorded on the appropriate SAE CRF
- followed through resolution by a study clinician
- reviewed and evaluated by a study clinician

Unanticipated Adverse Device Events (UADEs):

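### Complication collection closes at a floating contact about 2 to 4 weeks after biopsy, so the complication comparison has no common observation period

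*Combined protocol and SAP*

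**What the plan says.** - **End point.** Section 5.0 lists as secondary end point (ii): "Comparison of complication rates (Table 2) between arm A mpMRI+ and arm B". Aim 3 in Section 2.0 makes the same comparison.
- **Timing.** Adverse events are assessed at the biopsy. They are assessed again under the Section 5.0 item titled "POST-PROCEDURE EVALUATION/ END OF STUDY", where the entry reads "Can be done by telephone or clinical visit, usually 2-4 weeks post biopsy procedure". The pathology report is expected in the same 2 to 4 weeks.
- **Schedule.** Table 2, which covers both arms, has one post-biopsy column: "Post-Biopsy Follow-up/Study End (within 2-4 wks from biopsy) Follow-up can be done by telephone or clinical visit".
- **Close of collection.** Section 7.0: "AE/SAE information must be collected up until subject's completion of the study". Serious events that have been recorded are "followed through resolution by a study clinician".
- **Longest course named.** Table 3 lists among the common complications "Blood in your semen for up to 6 weeks".
- **Analysis.** Section 9.0 describes the trial as un-blinded. For complications it gives no cut-off day, no onset window and no rule for unequal observation time.
- **Scope.** Section 7.0 first restricts the adverse events collected to death and serious injury, and later speaks of collecting all of them.

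**The concern.** A complication rate means something only over a stated period. Here the period ends whenever the contact takes place. A man contacted on day 14 can be closed out on day 14, so a septic admission on day 16 need not be recorded. The same admission in a man contacted on day 28 would be. Following serious events to resolution does not help, because it applies only to events already captured. Section 7.0 also ties two of its criteria for a serious event, death and hospitalization, to the surveillance period that the protocol defines. The only such period the documents supply ends at this contact.

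At stake is a secondary comparison in a small un-blinded trial. Events are few, so one or two uncaptured ones can change the result. If contact timing happened to differ between the arms, part of any difference in complications would reflect observation time.

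**Working it through.** **No planned figure to reproduce.** Section 9.0 sizes the trial for Aims 1 and 2 only, and states no sample size or power for complications. The total of 80 men follows from 72 / 0.9 = 80.

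**Inputs from the documents.** Contact at 2 to 4 weeks, that is day 14 to day 28 (Section 5.0, Table 2). Longest named course 6 weeks, 42 days (Table 3). Rates of 10% for urinary infection and 2% for septicaemia (Table 3). About 25% of arm A assumed MRI-negative, and 36 men per arm, or 40 with the loss allowance (Section 9.0).

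**Step 1: spread of observation time.** 28 / 14 = 2, so a two-fold range between men. The word used in Section 5.0 makes the window typical and not binding, so the true spread could be wider.

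**Step 2: effect on an event rate.** Onset times are not given, so they are assumed here over a range. Let p be the true rate over 42 days and F(t) the share of events with onset by day t. The rate observed in men closed at day t is p × F(t).

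- Uniform onset: F(t) = t / 42.
- Early onset with mean parameter m days, truncated at 42 days: F(t) = (1 − e^(−t/m)) / (1 − e^(−42/m)).

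With p = 10% and the extreme split, one whole arm closed at day 14 and the other at day 28:

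| Onset assumption | F(14) | F(28) | Observed, day 14 | Observed, day 28 | Spurious difference |
|---|---|---|---|---|---|
| m = 3 days | 0.991 | 1.000 | 9.91% | 10.00% | 0.09 points |
| m = 7 days | 0.867 | 0.984 | 8.67% | 9.84% | 1.17 points |
| m = 14 days | 0.665 | 0.910 | 6.65% | 9.10% | 2.45 points |
| Uniform over 42 days | 0.333 | 0.667 | 3.33% | 6.67% | 3.33 points |

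With p = 2%, the differences are one fifth of these: 0.02 to 0.67 points.

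**Step 3: scale in men.** Arm A mpMRI+ would hold about 0.75 × 36 = 27 to 0.75 × 40 = 30 men. A shift of 3.33 points is 0.9 to 1.0 man. At a 2% rate, 80 × 0.02 = 1.6 septicaemia events are expected in the whole trial.

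**Step 4: does the 6-week figure enter the rate?** No. It describes how long blood in the semen may last. A man whose bleeding began before his contact already counts as having had the event. What is lost is the rest of its course, and no end point measures duration.

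**The case against.** The strongest case on the other side has four parts.

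1. *Six weeks is a duration.* A reader might infer from Table 3 that 14 to 28 of 42 days go unobserved and that close-out must therefore move to 6 weeks. The documents do not support this, because end point (ii) is a rate. This part stands in full.

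2. *Nothing shows that timing differs by arm.* A reader might infer bias because arm A mpMRI+ biopsies are done in the operating room by one urologist and arm B biopsies in clinic by several providers. That concerns who performs the biopsy, not when the man is contacted. Table 2 gives both arms one window, and Section 5.0 assigns adverse event assessment in both arms to one person. This stands to the extent that bias is only possible. But no fixed day rules it out in an un-blinded trial, and the contact shares its window with the arrival of the pathology result.

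3. *Larger figures rest on strong assumptions.* With a constant hazard and 10% risk by day 28, a day-14 close would show 1 − 0.9^(14/28) = 5.1%, a gap of 4.9 points. That takes the extreme split, a flat hazard for four weeks after a single procedure, and 10% reached by day 28. Anchored at day 42, the same hazard model gives 1 − 0.9^(14/42) = 3.45% against 1 − 0.9^(28/42) = 6.78%, a gap of 3.3 points. The larger gap should not be used as the estimate.

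4. *Equal observation could be had in the analysis alone*, by counting onsets to day 14 with no extra call. That would work if onset dates were recorded and no man was contacted before day 14. It would discard what is learned between days 14 and 28, and neither condition is in the plan.

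It is also fair to say that no sentence declares participation over at the first call. That follows from the item title, the Table 2 column label and the Section 7.0 collection rule read together.

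**Conclusion.** The point holds in limited form. Collection for end point (ii) and Aim 3 closes at a contact that is also the study end. Observation time can vary about two-fold between men, and events starting after an early contact need not be recorded. Variation between men within a shared window mainly adds noise. A bias between arms is possible, not demonstrated.

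For a true 10% rate, the spurious difference under the extreme contact split is about 0.1 to 3.3 points. Which end of that range applies depends on onset times that the documents do not give. If most complications start in the first days after biopsy, the effect on the rate is negligible. The primary end point and the sample size are untouched. This is a cheap improvement to a secondary comparison and does not threaten the trial's main conclusion.

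**What to change.** In the post-procedure part of Section 5.0, in Table 2 and in the collection rule of Section 7.0:

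- Name one fixed day after biopsy, the same for every man in both arms and no earlier than day 28, the end of the present window.
- Record the onset date of each complication.
- Count complications with onset from biopsy to that day, using one question list for all men.
- Close adverse event collection on that day. Where the results contact came earlier, add a short telephone call.

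A 6-week close-out is not needed for the rate.

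Two inconsistencies must be reconciled at the same time, or the fixed day will not help. Section 7.0 both limits adverse events to death and serious injury and calls for all of them, so it is unclear whether most Table 3 complications are recorded at all. End point (ii) also points to Table 2, the visit schedule, whose only event row is for unanticipated device events. The complications themselves are listed in Table 3.

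**Cost.** At most one call per man, so up to about 80, by a method the protocol already allows. With day 28 as the fixed day, study end moves by up to 28 − 14 = 14 days for men contacted at day 14. Protocol and consent wording change. The sample size does not.
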